###### **3.1.3.2 Delayed sleep onset latency (SOL) (i.e. cannot get to sleep within 30 minutes, three or more times a week)**

###### **3.1.3.3 Excessive wake after sleep onset (WASO) (i.e. nighttime awakenings lasting a total of at least 30 minutes, three or more times per week)**

##### **3.1.4. Neurocognitive impairment (i.e. score $\geq 84^{\text{th}}$ %ile of sibling normative data in at least one domain on the CCSS-NCQ)**

- 3.1.5. Regular access to the internet (at least 2-3 days per week)
- 3.1.6. Access to a desktop computer or a laptop
- 3.1.7. Access to a smart phone (android or iPhone), tablet or iPad with Bluetooth Low Energy BLE 4.2 or higher.
- 3.1.8. Ability to read and speak English

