### **3.5. Procedures for Identifying and Randomizing Research Participants**

Prior to initiating the study, team members will be trained on the protocol and study procedures. The background to the study, study procedures, consent processes for the online or the verbal consent, data transfer, and plans to monitor intervention integrity and data quality will be part of the training.

[figure not shown]
Following the study preparation, initial screening for eligibility, consent and additional eligibility verification for the research participants will begin. Once consented and eligibility is confirmed, participants will be randomized using a permuted-block method with random block sizes, stratified on sex, age (<40 vs.  $\geq 40$ ), and cranial radiation therapy (Y/N). Following randomization, participants will complete the remote cognitive assessment, will provide a blood sample using the Dried Blood Spot (DBS) method and wear a WHOOP wrist monitor for 7 to 11 consecutive days. Following the remote evaluation, they will receive a direct link to access the SHUTi program or online patient education (per randomization).

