## Neurocognitive Functioning

1) The Childhood Cancer Neurocognitive Questionnaire (CCSS-NCQ) is a 32 item self-report questionnaire evaluating 4 domains (8 questions per domain) of neurocognitive function: (1) memory; (2) task efficiency; (3) organization; (4) emotional regulation. The CCSSNCQ was developed specifically to address neurocognitive concerns of adult survivors of childhood cancer. It has been administered to over 12,000 non-brain tumor survivors within the CCSS cohort, and age- and sex-adjusted normative data are available from over 3,000 siblings of childhood cancer survivors. Extensive psychometric analysis of the CCSS-NCQ has been conducted, with the most recent involving Item Response Theory analysis and validation with traditional neuropsychological testing. The CCSS-NCQ will be used to screen participants for eligibility. For this study we will not utilize organization as an outcome because in our previous studies this domain has been shown to be less sensitive in detecting neurocognitive impairment. This questionnaire will be completed at baseline, post-intervention, and 6-month follow-up via the RICE Platform.

2) We will obtain a direct measure of cognitive function among participants using a remotely administered assessment (CNS Vital Signs). This remote assessment is completed using a desktop computer or laptop, and is self-administered. This assessment presents minimal risk to participants and enables them to complete the evaluation from their home.

instrument provides written instructions to the participant before beginning of each test. The tests evaluate cognition through evaluation of memory, attention, non-verbal reasoning, processing speed and reaction time. The cognitive assessment will include the following tests: Verbal Memory (VBM), Visual Memory (VIM), Finger Tapping (FT), Symbol Digital Coding (SDC), Stroop Test (ST), Shifting Attention (SAT) Continuous Performance (CPT). The total administration time is approximately 25-30 minutes.

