### 9.1. Summary of Primary and Secondary Objectives

#### Statistical Analysis

A randomized controlled design will be employed for the proposed study. We plan to enroll a total of 352 survivors (176 of each sex), and assuming 10% drop out by the post-intervention 9-week assessment, we will have a total of 320 survivors (160 of each sex) remaining for evaluation. Balance of patient characteristics between study arms will be evaluated and if necessary, adjusted comparisons will be carried out.

The primary endpoint of the study will be the ISI measure of insomnia severity represented as described above. The difference in score from baseline to post-intervention (10 weeks) and baseline to 6 months post-intervention will be calculated and the mean of these differences compared between study arms using linear regression (adjusted for stratification factors). The primary time point of interest will be at 10 weeks, with a secondary endpoint evaluating maintenance at 6 months after intervention. Due to potential sex differences in insomnia and cognition, *a priori* we plan to carry out all analyses and report results separately by sex. Our study is not powered to detect meaningful interaction effects, but if we deem that the effects are reasonably comparable between sexes we will consider presenting combined analysis to increase precision of the estimate. Because this is a randomized trial we expect analyses to be simple and directed towards ascertaining controlled and generalizable intervention effects. The primary endpoint will be considered significant at the two-sided 0.05 level. Estimates of intervention effects (mean differences) will be presented along with associated confidence intervals and two-sided p-values.

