Because mean scores do not reflect the number of survivors who have clinically significant insomnia symptoms, secondary analyses of sleep will compare the proportion of survivors who no longer meet the clinical criteria for insomnia (ISI  $\leq 7$ ) between study arms post-intervention (10 weeks) and at 6 months (noting that 100% of eligible participants will meet the criteria at randomization), using logistic regression models. Additional measures of sleep will also be summarized and compared (sleep diary, actigraphy, fatigue, daytime sleepiness) from baseline, post-intervention, and 6 months. Using the same analytic framework as above, we will evaluate the effect of study intervention on the secondary endpoints of neurocognitive impairment: patient reported (Task Efficiency, Memory, Emotional Regulation) and directly assessed (attention, memory, and executive function) with continuous outcome measures. Additional analyses relevant to secondary objectives focus on better understanding the associations and mediating relationships between the CBTi intervention, insomnia, neurocognition, emotional distress, cardiovascular risk indices and HRQoL (see Figure 2 for theoretical framework).

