### Power and sample size

We plan to enroll a total of 352 subjects, 176 of each sex), and assuming 10% drop out by the post-intervention 9-week assessment, we will have a total of 320 subjects (160 of each sex) remaining for evaluation. The

St Jude Children's Research Hospital

IRB NUMBER: 19-0121

IRB APPROVAL DATE: 05/04/2021

stratum, with 80 survivors per study arm, 80% power and  $\alpha$  of 0.05 for the primary endpoint comparison of the ISI, we will be able to detect a minimum effect size of 0.45. We will continue to enroll participants until we have 320 evaluable at 9 weeks. Assuming a total dropout of 20% by 6 months post-intervention, there will be approximately 70 survivors within each sex per study arm available for assessment, allowing detection of a 0.48 minimum effect size. If sex specific intervention effect estimates are comparable with each other, a combined analysis among the 320 survivors evaluable at 10 weeks will be sufficient to detect an effect size of 0.31, with 80% power and two-sided  $\alpha$  of 0.05. Secondary endpoints of neurocognition will have ability to detect the same effect sizes; secondary endpoint p-values will be presented using both a nominal significance level of 0.05 and adjustments for multiple comparisons using a false discovery rate methodology.

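### The neurocognitive endpoints are analysed as change scores without the baseline score of the same measure as a covariate, which gives up precision that the collected data could supply at no cost

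*Combined protocol and SAP*

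**What the plan says.** For the ISI, section 9.1 (Statistical Analysis) takes the change from baseline and has "the mean of these differences compared between study arms using linear regression (adjusted for stratification factors"). The neurocognitive endpoints follow by reference: "Using the same analytic framework as above, we will evaluate the effect of study intervention on the secondary endpoints of neurocognitive impairment". They are Task Efficiency, Memory and Emotional Regulation by self-report, and domains "directly assessed (attention, memory, and executive function) with continuous outcome measures". The last words show that the linear model is the one inherited, not the logistic model used for insomnia remission.

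The stratification factors come from section 3.5, where participants are "randomized using a permuted-block method with random block sizes, stratified on sex, age" group and cranial radiation. None of these is a cognitive score.

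The baseline scores will exist. Section 4.3 says of the CCSS-NCQ: "This questionnaire will be completed at baseline, post-intervention, and 6-month follow-up via the RICE Platform". Section 5.2 and its table schedule CNS Vital Signs at the same three visits.

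The power section carries the ISI figures over: "Secondary endpoints of neurocognition will have ability to detect the same effect sizes". It gives no SD and no correlation between visits for any cognitive measure.

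**The concern.** A change score fixes the coefficient of the baseline value at 1. Regression on the baseline lets the data choose that coefficient, so its residual variance cannot be larger, apart from one degree of freedom. When the correlation between visits is below 1 and the variances are equal, the best coefficient is below 1 and the change score carries avoidable noise.

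This matters because the plan has little precision to spare. All analyses are to be run separately by sex, at about 80% power for the stated effects, and the secondary p-values are also to be shown with a false discovery rate adjustment. Hypothesis 1.2.2.a rests on these models. So does the first step of the mediation test for 1.2.2.b, which needs an association between intervention and cognitive outcome.

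Three other clauses in 9.1 might seem to supply the covariate, but none does:

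- Adjusted comparisons may follow a check of balance between arms. This depends on the data and names no covariate.
- Cumulative methotrexate, cytarabine and cranial radiation doses enter the relevant analyses. These are exposures, not cognition.
- Baseline functioning is considered only in sensitivity analyses for missing data.

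**Working it through.** **Inputs from section 9.1.** Two-sided alpha 0.05 and 80% power. Within sex, 80 per arm post-intervention (effect 0.45) and 70 per arm at 6 months (0.48). Sexes combined, 160 per arm (0.31).

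**Reproducing the plan.** The minimum detectable effect is (1.960 + 0.842) × sqrt(2/n).

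- n = 80: 0.443 (noncentral t 0.446), stated 0.45
- n = 70: 0.474 (0.477), stated 0.48
- n = 160: 0.313 (0.314), stated 0.31

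The plan's figures are sound.

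**Variance with and without the baseline.** Let sigma be the SD of the score, equal at both visits, and rho the correlation between visits.

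- Change score: 2 sigma²(1 − rho)
- Adjusted for baseline: sigma²(1 − rho²)
- Ratio: f = (1 + rho)/2

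rho is not in the documents, so a range is shown.

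**Reading A: effect in SD-of-change units.** Power = Φ(d × sqrt(n/2) / sqrt(f) − 1.96), with f = 1 for the planned model. For n = 80 and d = 0.45, d × sqrt(n/2) = 2.846. The planned model gives Φ(2.846 − 1.96) = 81.2%. At rho 0.7, f = 0.85 and power is Φ(2.846/0.922 − 1.96) = Φ(1.127) = 87.0%.

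| n per arm, effect | planned | rho 0.5 (f 0.75) | rho 0.7 (f 0.85) | rho 0.8 (f 0.90) | rho 0.9 (f 0.95) |
|---|---|---|---|---|---|
| 80, 0.45 | 81.2% | 90.8% | 87.0% | 85.1% | 83.1% |
| 70, 0.48 | 81.1% | 90.6% | 86.9% | 84.9% | 83.0% |
| 160, 0.31 | 79.2% | 89.3% | 85.3% | 83.2% | 81.2% |

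For the first row, the noncentral t gives 80.8% rising to 90.4%, 86.6%, 84.7% and 82.7%. A simulation of 4,000 trials with two strata covariates in the model gave 81.4% to 90.8% at rho 0.5 and 80.2% to 85.7% at rho 0.7. In terms of sample size, the adjusted model matches the planned precision of 80 per arm with 80 × f = 60, 68, 72 or 76 per arm.

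**Reading B: effect in SD-of-score units.** The SD is now sqrt(2(1 − rho)) for change and sqrt(1 − rho²) after adjustment. For n = 80 and d = 0.45:

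| rho | change score | adjusted | gain in points |
|---|---|---|---|
| 0.3 | 67.2% | 84.7% | 17.5 |
| 0.4 | 73.8% | 87.4% | 13.6 |
| 0.5 | 81.2% | 90.8% | 9.6 |
| 0.7 | 95.7% | 97.9% | 2.2 |
| 0.8 | 99.4% | 99.7% | 0.3 |

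**Does selection at entry remove the gain?** Section 3.1.4 requires impairment "in at least one domain on the CCSS-NCQ", and section 3.3 identifies candidates from an earlier survey. Entry was simulated on any one of three domains at or above the 84th percentile, with assumed between-domain correlations of 0.4 to 0.6 and retest correlations of 0.5 to 0.8. The variance ratio was 0.78 to 0.93 when selection acted on the study baseline, and 0.76 to 0.92 when it acted on an earlier survey. Without selection it is 0.75 to 0.90. Power within sex at 80 per arm was about 83% to 90%. Selection shrinks the gain slightly but does not remove it.

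**The case against.** The strongest reply is that nothing here is wrong. Change from baseline adjusted for strata is a valid, unbiased comparison in a randomised trial. The stated effect sizes reproduce, and the plan says openly that it prefers simple analyses. That stands, and it is why the point concerns efficiency only. One more covariate does not make the model less simple.

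The size is also uncertain. rho is assumed, and the power text does not say which SD its effect sizes use. Some of that text is lost at a page break, so the missing unit may not be a gap in the plan. If the unit is the SD of the score and rho is 0.7 or more, the gain is about 2 points or less. This also stands, and both readings are shown for that reason.

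The balance check in 9.1 might catch a chance difference in baseline cognition. It would do so only after the data are seen and with a covariate still to be chosen, so it does not replace prespecification.

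Some stronger readings are tempting but unsupported:

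- A reader might infer bias from regression to the mean, because participants are selected for impairment. Such drift affects both randomised arms alike, and drift between the earlier survey and the study baseline is not in the change score.
- A reader might infer that selection leaves baseline spread nearly intact, or that it enlarges the loss. In the simulations, the per-domain baseline SD fell to between 0.79 and 0.98 of its unselected value, and the gain shrank slightly.
- A reader might treat 1.2.2.a as the leading secondary question, tested by every cognitive score. Section 1.2 does not rank its objectives, and 1.2.2.a is worded for reported symptoms post-intervention. It therefore concerns the CCSS-NCQ most directly. The computerised tests share the same modelling gap.

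**Conclusion.** The point holds as a free improvement. The cognitive models omit a covariate that is collected and that lowers residual variance for any rho below 1 at equal variances. On reading A, the gain at 80 per arm and 0.45 is roughly 10 points of power at rho 0.5, 6 at 0.7, 4 at 0.8 and 2 at 0.9. It is similar at 6 months and in the combined analysis. On reading B, the gain is largest at low rho and almost nil by 0.8.

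The documents do not support calling the trial underpowered for these endpoints. On reading A the planned model delivers its stated power. At 80 per arm it falls short only on reading B with rho below about 0.5, and the documents establish neither condition.

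The result assumes equal variances at the two visits, a linear relation between baseline and follow-up, and the rho values shown.

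**What to change.** In section 9.1, state that each continuous cognitive measure, at 10 weeks and at 6 months, is regressed on arm, the stratification factors and the baseline value of that same measure, within sex and in any combined analysis. The outcome may be the follow-up score or the change: with the baseline in the model the arm coefficient is the same, and it remains a mean difference on the original scale.

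The simplest edit is one general sentence in the primary-endpoint paragraph, saying that every continuous outcome is adjusted for its own baseline. The neurocognitive endpoints then inherit it through the existing cross-reference. Naming baseline ISI alone would not be enough, because it would not bring baseline memory or attention into the cognitive models.

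No separate rule on timing is needed. Section 3.5 places the baseline remote evaluation after randomisation but before the program link is sent, and a change score relies on that same baseline.

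The cost is one sentence and one degree of freedom per model, with no new data and no change in what is estimated.

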direct relationships between change in ISI (baseline to post-intervention) with emotional distress and cardiac health indices at postintervention time points and with HRQoL measures. To establish whether a mediation relationship exists, we will follow standard methodology by 1) establishing that there is an association between the causal variable (e.g. CBTi intervention) and the outcome (e.g. neurocognitive impairment), 2) establishing the association between the causal variable and the mediator and 3) showing that the mediator is associated with the outcome variable in a model with the causal variable included and 4) in the same model as used to evaluate step 3, determine that the relationship between the causal variable and the outcome variable is attenuated by inclusion of the mediator in the model. We do not expect to observe complete mediation in any of our investigations. Specifically, the above methodology will be used to test hypothesis 1.2.2.b with the causal variable defined as CBTi intervention, mediator as change in insomnia (ISI) and outcomes as neurocognitive indices. Hypothesis 1.2.2.c will consider change in insomnia as the causal variable, neurocognitive function indices, emotional distress symptoms and cardiovascular risk indices as mediators for the outcome HRQoL at 6 months. In addition to the stepwise model-based approach outlined above, we will also evaluate relationships using Structural Equation Modelling (SEM) approaches to evaluating mediation, which would allow simultaneous evaluation of the multiple pathways and classes of variables together in a single model, with improved power, allowing estimates of direct and indirect effects calculated from each. All effects size estimates (mean differences and/or odds ratios) will be presented along with associated confidence intervals and two-sided p-values, both unadjusted and adjusted for multiple comparisons. Primary therapies for childhood cancer have been associated with insomnia and study outcomes (neurocognitive morbidities, emotional distress, cardiovascular risk). Because our study inclusion criteria require that survivors have observed neurocognitive deficits we do not expect differential responses to SHUTi by previous childhood cancer treatment exposures. However, chemotherapy exposures and radiation doses are abstracted from medical records and cumulative doses of methotrexate (high dose and intrathecal), cytarabine, and cranial radiation will be included as covariates in relevant analyses. In addition, we will conduct sensitivity analyses to examine their contributions to treatment response.

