
We have planned for 20% attrition over the course of the 6-month study. However, if there is a substantial amount of missing data at 9 weeks or 6 months we will examine the characteristics of survivors who have complete data with those who do not. Depending upon the pattern of missing data, we will conduct sensitivity analyses to assess the impact of missing data on the results. We will consider factors such as demographic and treatment variables as well as premorbid baseline functioning in our sensitivity analyses.

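### Models that explain follow-up health by change in ISI name no adjustment for baseline ISI or the baseline outcome, so their slopes are biased wherever the two are correlated at baseline

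*Combined protocol and SAP*

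**What the plan says.** Two parts of Section 9.1 (Statistical Analysis) use change in ISI as an explanatory variable that was not randomised.

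- **Direct associations.** The plan will look at "direct relationships between change in ISI (baseline to post-intervention) with emotional distress and cardiac health indices at postintervention time points" "and with HRQoL measures". In the available text this sentence begins part-way through, at a page break. Its outcomes for distress and cardiac health are placed at post-intervention time points. For HRQoL it does not say whether a level or a change is meant.
- **Second mediation model.** This text is intact: "Hypothesis 1.2.2.c will consider change in insomnia as the causal variable", with neurocognitive, distress and cardiovascular measures "as mediators for the outcome HRQoL at 6 months". The outcome is a follow-up level. The pathway is the one that Section 1.2 lists as hypothesis 1.2.3.b.

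The four mediation steps name only the cause, the mediator and the outcome. The covariate sentence says that "cumulative doses of methotrexate (high dose and intrathecal), cytarabine, and cranial radiation will be included as covariates in relevant analyses". The arm comparison is adjusted for the stratification factors, with further adjustment if the arms prove unbalanced. Baseline status appears once more, for missing data, as "premorbid baseline functioning in our sensitivity analyses".

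Sections 4.3 and 5.2 show that ISI, PHQ-9, GAD-7, CCSS-NCQ, the blood-spot markers and HRQoL are all measured at baseline.

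**The concern.** A change score carries its own baseline with the opposite sign. A survivor with a high starting ISI has more room to fall and tends to regress towards the mean, so large improvement goes with a bad start. If a bad start on ISI also goes with a bad start on distress or quality of life, and those outcomes are fairly stable, the largest improvers can still have the worse follow-up values. A model of the follow-up level on change in ISI alone mixes this pattern with any real benefit of better sleep.

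Randomisation does not protect these models, because change in ISI is not assigned. They bear on hypotheses 1.2.2.c, 1.2.3.a and 1.2.3.b, which carry the theoretical model in Section 2.2. The first mediation step requires an association between cause and outcome. An attenuated slope can fail that step, and real mediation would then be declared absent.

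**Working it through.** **The plan's own figures.** The documents state no effect size or power for these models, so only the sample sizes can be taken from them. The power section's detectable effects reproduce (normal and t calculations, two-sided 0.05, 80% power):

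- 80 per arm: 0.443 to 0.446, against the stated 0.45.
- 70 per arm: 0.474 to 0.477, against 0.48.
- 160 per arm: 0.313 to 0.314, against 0.31.

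At 6 months, 70 per arm per sex gives 4 × 70 = 280 overall and 2 × 70 = 140 within one sex. The plan intends all analyses by sex.

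**Model (baseline-SD units, outcomes scaled so that higher is worse).** X0 and X1 are ISI before and after; D = X1 − X0; Y0 and Y1 are the outcome before and after.

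- X1 = r·X0 + τ·arm + error
- corr(X0, Y0) = c
- Y1 = ρ·Y0 + β·D + error

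A positive β means that a larger fall in ISI goes with a better outcome. The slope of Y1 on D alone is

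β − ρ·c·(1 − r) / Var(D), with Var(D) = 2(1 − r) + τ²/4.

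**Assumed values (none is in the documents).** r = 0.5 and τ = 0 give Var(D) = 1 and a change-baseline correlation of −0.5. Outcome stability ρ is 0.6. The bias is then −0.6 × c × 0.5 = −0.3c.

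| c | Bias | Slope if true β = 0.25 | Power, n=280 | Power, n=140 | Wrong-direction significance if β = 0, n=280 | Same, n=140 |
|---|---|---|---|---|---|---|
| 0.1 | −0.03 | 0.22 | 96% | 74% | 7% | 5% |
| 0.3 | −0.09 | 0.16 | 76% | 47% | 33% | 19% |
| 0.5 | −0.15 | 0.10 | 39% | 22% | 69% | 45% |

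With both baseline values in the model, the slope returns to 0.25. Power is 99% at n=280 and 88% at n=140, and total rejection under no link is about 5%. An unbiased two-sided 0.05 test would be significant in the wrong direction in 2.5% of trials. The percentages are simulated (2,000 to 4,000 trials), and repeat runs move single entries by up to about 3 points.

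A hand check of the last row under no link: the correlation of D with Y1 is −0.15. At n=280 the expected t is 0.15 × √278 / √(1 − 0.15²) = 2.53 in size, and Φ(2.53 − 1.97) = 0.71; the runs gave 69% to 72%. At n=140 it is 1.78, and Φ(1.78 − 1.98) = 0.42; the runs gave 43% to 45%.

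**Sensitivity.**

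- With r 0.3 to 0.7, c 0.3 to 0.6, ρ 0.5 to 0.8 and τ 0 to −0.8, the bias runs from −0.06 to −0.24. It is zero if c = 0.
- The expected sign reverses only when β is below ρ·c·(1 − r)/Var(D). At r = 0.5 and τ = −0.8, a true 0.10 becomes −0.05 (c 0.5, ρ 0.7), while a true 0.30 becomes 0.09 to 0.24 across the cases run.
- Adjusting for arm alone does not help. At β = 0, r = 0.5, τ = −0.8, c = 0.5 and ρ = 0.7, the slope is −0.149 without arm and −0.172 with it.
- If Y1 depends on the ISI level reached and not on the change, the baseline outcome alone is not enough. At c = 0.5 and ρ = 0.7 a true 0.20 is then estimated as 0.133, and adding baseline ISI restores it.
- If the outcome is itself change from baseline, the bias is +(1 − ρ)·c·(1 − r)/Var(D). With the table's values that is 0.4 × c × 0.5, or +0.06 to +0.10 for c 0.3 to 0.5, in the favourable direction.

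**The case against.** **Omission as fact.** A reader might infer that the plan leaves baseline values out of all these models. The documents do not support that. The start of the association sentence is missing and may have named the model and its covariates. The covariate sentence deals with earlier cancer treatment and is limited to relevant analyses; it is not offered as a full list. The structural equation model is left open, so baseline paths are neither promised nor excluded. What stands is narrower: the 6-month HRQoL model is described in intact text, and no visible text names a baseline adjustment for it. The provision for imbalance between arms does not fill the gap, because this bias arises with perfectly balanced arms.

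**Reversal as the expected result.** A reader might infer that the results will come out backwards. That needs a material baseline correlation and a small or null true effect. Section 2.2 supports a correlation for distress: disrupted sleep had an odds ratio of 4.4 (95% CI 3.1 to 6.3) with elevated depressive symptoms. For cardiac indices it reports associations but no correlation sizes, and these may be weak. At c = 0.1 the effect is minor.

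**Every model with change in ISI.** The mechanism does not carry over unchanged to hypothesis 1.2.2.b. There the arm is the cause, change in ISI is the mediator, and the neurocognitive outcomes follow the change-from-baseline framework.

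**Importance.** These are secondary analyses, and objective 1.2.3 is worded as exploratory. That stands and limits the weight of the point.

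**Conclusion.** The point holds in limited form. As described, regressing a follow-up level on change in ISI gives a slope biased against the expected direction whenever baseline ISI and the baseline outcome are correlated and the outcome is stable. It is firmest for the 6-month HRQoL model, likely for distress if the missing words add no baseline terms, and possibly negligible for cardiac indices. Moderate true effects are attenuated; small or null ones can change sign. The sizes in the table rest on assumed correlations and should be read as a range. Confidence is medium. The randomised ISI comparison, its significance level and the sample size are not affected.

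**What to change.** Add to Section 9.1 that every model with change in ISI as the causal variable, including the structural equation model, adjusts for baseline ISI, the baseline value of the outcome and of each mediator, and study arm. State for each outcome, HRQoL in particular, whether it is analysed as a level or as a change. In the 1.2.2.b model, where change in ISI is the mediator, include baseline ISI and the baseline neurocognitive score.

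The cost is a few sentences of analysis-plan wording. All the baseline values are already collected, and neither the sample size nor the visit schedule changes. This is a free improvement that should be made before these analyses are run.
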